The RCT design will be used to test the efficacy of technology-enhanced TPC for FCGs on outcomes related to the FCGs' experience and determine the impact on costs from a societal perspective. After informed consent is obtained, FCGs will be randomly assigned to one of two groups by computer-generated randomization lists: 1) the experimental group or 2) a "usual care" or control group. Consistent with transitional care models,^{142,143} the intervention period will continue for 8 weeks after care recipients are discharged from the hospital.

Setting

The setting for this study is the Mayo Clinic Hospitals in Rochester and Mankato Minnesota and LaCrosse Wisconsin. While patients at the Mayo Clinic Rochester Hospital come from all regions of the US and many foreign countries, the majority (80%) come from within a 120-mile radius of Rochester. The same holds true for the more community-based hospitals in Mankato and

LaCrosse. Of the 31 counties in the major catchment area of the clinic, 26 are designated as rural or federally designated medically underserved areas.^{144,145}

The Palliative Care consulting service is available to any patient hospitalized at Mayo Clinic Hospital — Rochester, Mayo Clinic Health Systems in Mankato and/or LaCrosse. The Mayo Clinic Rochester service is organized into 3 teams. Each team has a physician and an advanced practice clinician, plus students. On average there are 6-10 new consults per day. The palliative care teams meet daily to discuss new and continuing patients. Dr. [REDACTED] (Co-I), [REDACTED] (pharmacist), [REDACTED] (SW) and [REDACTED], (APN) are members of the palliative care consulting service and members of our research team.

The Palliative Care consulting service in the Mayo Clinic Health System hospitals in Mankato and /or LaCrosse is smaller and includes one team for each site. The research coordinator will work independently of the Palliative care clinic team at these hospitals.

Sample – Target population

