A study nurse will develop an individualized FCG plan of care based on their assessment of FCG risks, needs, strengths, and preferences.¹⁵⁰ A unique plan of care to support FCGs includes: (1) a wellness plan to meet their own self-care (preventive and health-related physical and emotional wellness needs) and concerns during the transition period and (2) help for the FCG to meet the care recipient's needs. FCG Readiness Plans are key components of the FCG plan of care providing anticipatory guidance to address self-care needs and to meet common symptom management challenges for use by FCGs. The nurse will assist the FCG in implementing the plan of care and refine the plan of care to accommodate changing caregiving needs throughout the 8-week intervention through FCG advocacy, teaching, guidance, and counseling through in-person visits (during the hospital stay), and video visits and phone contacts at home. A copy of the individualized self-care plan will be provided to the FCG at the end of the intervention. [name] (Co-I) contributes the necessary expertise to oversee and train the study nurses in the TPC for FCGs intervention.

The TPC for FCG intervention will be provided by experienced, certified palliative care registered nurses. Review and recommendations of plans of care will be provided weekly and more often as needed by a study palliative care team (physician, pharmacist and social worker). Team meetings will focus collectively on identifying and meeting the unique caregiving and self-care needs of each FCG incorporating tenets of both transitional care and palliative care (Figure 2). Review and updates of the plans of care will be conducted with the FCG and other clinicians on the study team to meet mutually agreed and attainable goals.

Part 1: Pre-discharge intervention. The study nurse will make the first pre-discharge I visit with the FCG within 24 hours of study enrollment either in person or via video and every other day visits with the FCG during the remainder of the care recipient's hospital stay. The study nurse will have

Figure 2. Technology-Enhanced Transitional Palliative Care for Family Caregivers
Intervention Objectives

Caregiving in Palliative Care ^{103,108}	Caregiving in Transitional Care ^{18,143,149}	

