1. Education on palliative care 2. Self-care for the caregiver a. Balancing family, self, and caregiving responsibilities b. Sleep and rest c. Accepting help 3. Education on role of caregiver in palliative care context 4. Strategies to respond to care recipient physical symptoms and emotional issues 5. Goal setting and problem solving 6. Advance care planning	1. Education regarding care recipient medications, administration, and side effects 2. Discuss importance of follow-up with primary care, specialty providers 3. Education regarding indications of changes in care recipient condition and how to respond 4. Follow-up visit/Reconnect to primary care provider 5. Integrated care plan with health & community services 6. Communicating with healthcare providers	
Timeframe of Activities		
Each Hospital Day	Post-Discharge/Community based Visits	
APN daily interaction including transition planning with FCG	Weeks 1-4 Minimum of 2 virtual visits/week by APN with FCG, phone calls as needed	Weeks 5-8 Minimum of 1 virtual visit/week by APN with FCG, phone calls as needed

access to all baseline data collected to assist with assessment and care planning (See Table 1 below for variables and measures). During the pre-discharge visits the nurse will: (1) assess the FCG's physical and emotional self-care needs, including the involvement of secondary caregivers and/or formal service providers to support the FCG and develop a FCG wellness plan; (2) assess the FCG's knowledge and skills for skillful caregiving; (3) begin transitional care planning by working with the FCG, the palliative care consulting service and acute care staff, and local community service providers; and (4) develop individualized FCG Readiness Plans (adapted from Hospice & Palliative Nurses Association and AARP materials)^{2,117} to anticipate caregiving needs that may arise when they return home. On the day of care recipient's discharge, the nurse will confirm the FCG's understanding of caregiving needs, physical and emotional readiness for caregiving, and confirm that plans for FCG self-care and respite are in place.

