interpersonal conflict with potential violence or risk for self-neglect. Standard best practice protocols on assessing depression risk and self-harm will be followed. These include:

- a. General and specific screening tools about neglect or mistreatment will be completed

- a) With any suspicion of risk for self-harm, violence, or safety, the person with the closest knowledge (who talked or visited with the care recipient or caregiver) immediately contacts MN, WI or IA Adult Protective Services.
- b) Police will also be contacted if there is an imminent or immediate threats
- c) If intervention nurse or study social worker determine no suspicion for harm, coping skills and resources are discussed and when necessary, referral to palliative care/hospice team social worker.
- d) All conversations and decisions are documented into study records.

Table 1. Framework concepts, variables, timing, and estimated burden

Concepts	Variables and Measures	Timepoints	Estimated Burden
Sample Characteristics			
	Age, gender, race/ethnicity, marital status, education, relationship of FCG to care recipient, how long the FCG has been providing care to the care recipient, any computer/Smartphone experience and availability, diagnoses, medications,	Baseline	2-6 minutes
Properties of the Transition			
	Mutuality, ¹³⁴ Single items for relationship of FCG/care recipient; Caregiving demand ¹²⁹	Baseline	2-6 minutes
Transition Conditions (Facilitators or Barriers)			
Characteristics	Spiritual/Religious beliefs, ¹²⁸ Time available for caregiving (FCG Responsibilities & Demands), ¹²⁹ Decision making preference, ¹³⁰ Health literacy, ¹³¹ Income (single items), FCG Support Needs, ¹³² Hospital Discharge Readiness, ¹³³ FCG Personal Health Problems ¹²⁹	Baseline	5-12 minutes
Patterns of Response (Outcomes)			
Aim 1	Preparedness for caregiving, ¹³⁴ Communication skills, ¹³⁵ Satisfaction with care - CG-PACIC ^{136,137}	Baseline, 2, & 8 weeks	6-10 minutes
Aim 2	Quality of Life (CG QOL Scale-Cancer), ^{9,138} Coping, ¹³⁹ Depression, ¹⁴⁰ Burden (Bakas Caregiving Outcomes Scale), ¹⁵⁹ Patient Outcome Scale-Carer ¹⁶⁰ ,	Baseline, 2, & 8 weeks	17-20 minutes
Aim 2	Depression, ¹⁴⁰ Burden (Bakas Caregiving Outcomes Scale), ¹⁵⁹ Positive Aspects of Care (6 months only); open-ended study satisfaction	6 months	6-10 minutes
Aim 3	Healthcare Utilization and Cost (Ambulatory and Home Care Record)	Monthly, 6 months	30 minutes

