Properties of the transition. Guided by the theoretical framework for the study, measures of properties of the transition include the quality of the FCG/care recipient relationship (Assessment of Mutuality^{121,134,161-163}) and caregiver demand (hours of caregiving and length of time caregiving¹²⁹). Variables related to the properties of the transition serve as control variables or will be considered as covariates in the analysis.

Transition conditions (facilitators and barriers). Measures of facilitators/barriers also serve as control variables and include spiritual/religious beliefs,¹²⁸ time available for caregiving (due to other FCG responsibilities and demands),¹²⁹ decision making preferences,¹³⁰ health literacy,¹³¹ income, FCG support needs,¹³² readiness for hospital discharge¹³³ (measured at hospital discharge), and FCG personal health problems (if any).¹²⁹

Aim 1: Evaluate the effect of a technology-enhanced TPC care model on caregiving preparedness, communication with clinicians, and satisfaction with care for FCGs.

1. Preparedness for caregiving. The Preparedness for Caregiving Scale^{134,161,163} captures how well FCGs feel they are prepared for the multiple aspects of the caregiving role, using a 4-point response set ranging from 0 ("not at all") to 4 ("very well"). A mean score is calculated; higher scores indicate greater preparation for caregiving.¹⁶³ Cronbach alphas of 0.88-0.93 are reported.¹⁶³

2. Communication skills. The Communication with Physicians scale¹⁶⁴ will be used to measure the communication skills of the FCG. Originally designed for chronic disease self-management behavior, the scale has 3 questions targeting how often the FCG prepares a list of questions for the doctor, asks questions, and discusses personal problems across a 6-point response set ranging from “never” to “always.” Scores range from 0-5 with higher scores indicating better communication. Internal consistency and test-retest reliability coefficients are good (0.73, 0.89, respectfully).¹⁶⁴

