Aims 1 and 2. Statistical analyses of Aims 1 and 2 will be performed in a similar manner. Every FCG will be evaluated using various scales and survey instruments at baseline, 2 weeks, and 8 weeks post patient discharge (Table 1). We will use a response-feature analysis as our primary approach in analyzing these repeated measures data.¹⁸¹ For each FCG, the magnitude of the scores from the respective instruments will be plotted versus time (measured in months); least squares regression will be used to estimate a participant-specific rate of increase in points per month. This slope parameter estimate will be used as the response feature for each participant and is the primary endpoint for this study. The primary analysis of this endpoint will be analyzed using a two-sample t-test or Wilcoxon rank-sum test, as appropriate. The endpoints will also be analyzed using a fixed-effects linear regression model. This model will use the estimated regression-slope response-feature as the dependent variable and have independent variables consisting of intervention (yes, no) as well as any baseline covariates such as FCGs’ age, employment status, etc. These analyses will adjust for any possible imbalances in these baseline covariates among FCGs that occur due to the randomized assignment to the intervention. This analysis approach will hold for those endpoints collected only at two time points (i.e., baseline and 8 weeks).

Aim 3. Descriptive statistics, including mean, median, and standard deviation (minimum and maximum) for the utilization measures (i.e., hospitalizations and ED visits) will be provided. Considering the count nature of the utilizations, and to also account for any potential differences between the baseline characteristics of the care recipients in the two study arms, we will use Poisson regression to model various utilization outcomes.¹⁸² We expect that the gains (decreased healthcare utilization and costs) will be sustained beyond the enrollment period. Therefore, both descriptive and multivariable-adjusted measures will be estimated for the intervention period and the subsequent months post-intervention. A limitation of this economic approach will be the memory recall of the FCGs. We will provide a worksheet similar to Table 2 for all participants to help them track services and costs.

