- Day of discharge
 - Confirm FCG and patient readiness for discharge – understanding of patient care needs, physical and emotional readiness for caregiving, plans for FCG self-care and respite are in place
 - Assure Palliative Care Team consensus on post discharge FCG Readiness Plans to support caregiver activities on behalf of the patient
 - Implement and coordinate Transitional Care Plan
 - Schedule first virtual visit
- Document all problem-related assessments/interventions for each FCG encounter on study documentation forms

Part 2. In-Home

- Provide ongoing education, guidance and support to FCG for Transitional Care Plan to develop caregiving skills described above
- Coordinate the implementation of transitional care plan
 - Communicate with local community resources to assure support services are in place and effective
 - Reassess continued appropriateness/outcomes of FCG Readiness Plans
 - Identify and address any new problems that develop
- Reaffirm and provide education and anticipatory guidance for use of appropriate FCG Readiness Plans
- Collaborate with primary care provider/specialty provider who will provide primary care related to goals of care
- Coach FCG in preparation for care-recipient physician office visits
- Provide additional virtual visits/phone calls to support FCG as needed during:
 - Transfer to hospice
 - Permanent nursing home placement
 - Death of care-recipient
- Document all assessments/interventions for each FCG encounter on study documentation forms
 - The pre-discharge protocol will be reinstated for the duration of the hospital stay. Virtual visits will begin again after hospital discharge.

Review case weekly with palliative care study team members (MD, SW, Pharm)

Final virtual visit - complete FCG transition to ongoing family, community and health care support

If patient is rehospitalized during the 8-week study period

Conducting TPC for FCG Intervention Initial and Ongoing during Part 1 and Part 2

Assessments and Monitoring – Assess FCG's priority emotional, self-care needs and caregiving support needs

- Psychosocial
 - Mental health – anxiety or depression
 - Grief/anticipatory grief
 - Spirituality
 - Communicating with Healthcare & Community Resources
 - Social Contact
 - Role Change
 - Interpersonal Relationship
 - Other
- Self-Care Needs
 - Nutrition
 - Physical activity
 - Sleep and Rest
 - Personal care
 - Condition specific needs (cardiac, respiratory, pain etc.)
 - Medication regimen

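### Readiness for hospital discharge is a control variable timed at discharge in the text but at Baseline in Table 1, so the adjusted model may condition on something that assignment can change

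*Combined protocol and SAP*

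**What the plan says.** Under Variables and Their Measurements, the paragraph on transition conditions states: "Measures of facilitators/barriers also serve as control variables". Readiness for hospital discharge is in the list that follows, and its timing is given in the words "measured at hospital discharge), and FCG personal health problems (if any". No other item in that list has a timing of its own.

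Table 1 places "Hospital Discharge Readiness" in the Transition Conditions row, whose timepoint is Baseline.

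Research Design states: "After informed consent is obtained, FCGs will be randomly assigned to one of two groups by computer-generated randomization lists". In the experimental arm, Part 1 (Pre-discharge intervention) sets the nurse's first visit "within 24 hours of study enrollment either in person or via video and every other day visits with the FCG" for the rest of the hospital stay. These visits include developing individualized Readiness Plans. On the day of discharge the nurse confirms, among other things, "physical and emotional readiness for caregiving, and confirm that plans for FCG self-care and respite are in place". Appendix A lists as a task for that day: "Confirm FCG and patient readiness for discharge".

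The Analytical Plan for Aims 1 and 2 makes an unadjusted two-sample t-test or Wilcoxon rank-sum test on participant slopes the primary analysis. It adds a linear regression of the slopes with "independent variables consisting of intervention (yes, no) as well as any baseline covariates such as" age and employment status, in order to deal with chance imbalance at baseline.

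**The concern.** A covariate can correct chance imbalance only if assignment could not have influenced it. Readiness recorded at discharge does not meet that condition, because the experimental arm has by then had nurse contact aimed at preparing the caregiver. The protocol's own framework also treats transition conditions, readiness for discharge among them, as facilitators of or barriers to the transition. It thus expects readiness to bear on the outcomes.

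If such a variable enters the adjusted regression, the intervention coefficient leaves out whatever part of the effect runs through readiness. Unmeasured causes shared by readiness and outcome can distort the remainder in either direction. A gap between the adjusted and primary results could then be read as the correction of baseline imbalance when it is not.

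**Working it through.** **1. The two timings.** The transition-conditions paragraph says at hospital discharge. Table 1 says Baseline. Variables and Their Measurements describes baseline as following consent and preceding discharge. The two entries could nearly coincide in a short stay, but they are not the same timepoint.

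**2. Order of events for a discharge value.** Enrollment takes place in hospital, at the palliative care consult. Consent comes next and randomization follows consent. In the experimental arm the first nurse visit falls within 24 hours of enrollment, and visits continue until discharge. A discharge value therefore follows randomization in both arms and nurse contact in one.

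**3. Route into the model.** Three statements bear on this:
- The transition-conditions paragraph gives these measures the role of control variables and attaches no condition. The neighbouring paragraph on properties of the transition is looser, allowing that its variables may instead be considered as covariates.
- Table 1 labels readiness Baseline.
- The Analytical Plan accepts baseline covariates from an open list, with examples and no rule that they precede randomization.

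An analyst who follows all three could include readiness in good faith. None of them names readiness as a term in the regression, so inclusion is permitted, not prescribed.

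**4. The plan's own figure.** Inputs from Sample Size and Power Calculations: 100 per group, effect size 0.487, two-sided alpha 0.01, two-sample t-test. Power is 0.799 by the noncentral t distribution and 0.807 by the normal approximation. The stated 80% reproduces. It belongs to the unadjusted comparison, which contains no covariate.

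**5. What inclusion would do.** Put the slope outcome and readiness each on a scale with within-arm SD 1. Let a be the difference in mean readiness between arms caused by assignment, and b the within-arm slope of outcome on readiness, whether it arises from a causal effect or from shared causes. Then

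adjusted difference = total difference − a × b.

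The bias is zero if a = 0 or b = 0, and its sign depends on the signs of both. The documents give neither quantity. With the total difference set at 0.487 and both inputs assumed:
- a = 0.2, b from −0.5 to +0.5: 0.487 + 0.100 = 0.587 down to 0.487 − 0.100 = 0.387.
- a = 0.5, b from −0.5 to +0.5: 0.487 + 0.250 = 0.737 down to 0.487 − 0.250 = 0.237.

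A simulation of 4,000 trials with a = 0.5 and b = 0.3 gave a mean of 0.485 unadjusted and 0.334 adjusted; the formula gives 0.487 − 0.150 = 0.337. This confirms the algebra only. The range follows from the assumed inputs and says nothing about how large the bias would be in this trial.

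**The case against.** The strongest reply is that the regression is restricted to baseline covariates and never mentions readiness. If Table 1 is right and readiness is taken at baseline, the specific concern largely goes. If the text is right and it is taken at discharge, the word baseline argues against including it. This stands to the extent that inclusion is not certain. It does not close the matter, because the control-variable role is stated separately and the Baseline label would let a discharge value through.

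A second reply is that the nurse's day-of-discharge task is to confirm readiness, which is a check and does not itself raise it. That is fair for the task alone. The earlier visits, however, include education, planning and Readiness Plans, which could plausibly raise it. The instrument is not reproduced in the text, so its overlap with the intervention content cannot be verified. The supported statement is that assignment can affect readiness, not that it will.

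A reader might also infer that readiness is the only covariate with this weakness. The documents do not show that. Baseline collection and randomization both follow consent and are not ordered against each other, and the Enrollment paragraph asks for baseline data before discharge only where possible. The nurse's access to baseline data does not prove that all of it came before the first visit.

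**Conclusion.** The point holds for the additional adjusted regression. The documents contradict themselves on when discharge readiness is measured, and they permit a measure taken after randomization, and open to the intervention, to be used as an adjustment covariate. If it is so used, the intervention coefficient does not estimate the full effect of assignment.

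The bias has no derivable size or direction; the range shown above illustrates the mechanism and should not be used to grade the problem. The conclusion assumes that readiness is measured at discharge and is entered in the model. If it is collected before randomization, this concern falls away and only the wording needs correction.

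A reader might infer that the trial's main result or its power is compromised. It is not: the primary t-test or Wilcoxon analysis uses no covariates and the 80% figure stands. Nor do the documents support saying that the adjusted analysis will be biased, only that as written it may be.

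**What to change.** - Reconcile the timing of discharge readiness between Table 1 and the transition-conditions paragraph.
- If it is measured at discharge, remove it from the control variables and do not adjust for it in the regression for Aims 1 and 2. It may be reported descriptively by arm as a process measure.
- If it is measured at baseline, correct the transition-conditions paragraph.
- State in the Analytical Plan for Aims 1 and 2 that adjustment uses only covariates that assignment cannot have affected: those collected before randomization or before first intervention contact, or fixed characteristics such as age.

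The change is wording in Table 1, the transition-conditions paragraph and the Analytical Plan. The primary analysis and the sample size do not change. There is a small downside: because baseline collection is not ordered against randomization, the collection dates of questionnaire covariates must be checked, and a few values collected late may not be usable for adjustment.
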